Few studies have evaluated PFHxS exposures and the risk of cancers and other adult diseases. Although 9 10 epidemiological studies have primarily evaluated PFOA and PFOS, there remain considerable data gaps 11 concerning the health effects of exposures to these chemicals in adults. There have been inconsistencies 12 in findings across studies and limited sample sizes in some studies. For some adverse outcomes, only one or a few studies have been conducted. Finally, except for the C8 studies, there are no published individual-13 14 level epidemiological studies in adults that have evaluated the health effects from exposures to PFAS-15 contaminated drinking water. Therefore, additional research is necessary to determine whether drinking 16 water exposures to PFHxS, PFOS, and PFOA increase the risk of non-cancer diseases. The proposed scope 17 of the funding and sample size estimated for this health study would be too small and insufficient to evaluate cancer health outcomes. 18

19 **2.5.2 Hypotheses**

For children (aged 4-17 years), the Multi-site Study will evaluate the following main hypotheses, following
the outline of the biochemical analytical plan (**Attachment 2**):

22

23 Higher serum levels of PFOA, PFOS, PFHxS, or other PFAS are associated with:

- Lipids (higher total cholesterol, low-density lipoprotein, and triglycerides, and higher prevalence
 of hypercholesterolemia; higher prevalence of obesity).
- Impaired renal function (a higher level of uric acid, a higher prevalence of hyperuricemia, and a
 lower estimated glomerular filtration rate (eGFR).

1	3.	Liver function/damage biomarkers (alanine transaminase (ALT), γ -glutamyltransferase (GGT),
2		direct bilirubin, cytokeratin-18 (CK-18)), and non-alcoholic fatty liver disease/steatohepatitis.
3	4.	Glycemic parameters (glucose, insulin, glycosylated hemoglobin (HbA1c), auto-antibodies
4		[glutamic acid decarboxylase (GAD-65) and islet antigen 2 (IA-2)], C-peptide, pro-insulin) and
5		diabetes (type 1 and 2).
6	5.	Measures of thyroid function (differences in thyroid stimulating hormone - TSH, total thyroxin -
7		TT4, free thyroxin - FT4, and TT3; higher prevalence of hypothyroidism/hyperthyroidism).
8	6.	Differences in sex hormones, growth and sexual maturation (testosterone, estradiol, and sex
9		hormone-binding globulin (SHBG); insulin-like growth factor - 1 (IGF-1), age at menarche, delayed
10		puberty).

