- ____No, it is irregular
- ____No, she does not have a period \rightarrow go to Question F10
- ____Don't know \rightarrow go to Question F10

F7. How many days has been your daughter's cycle on average during the last year?

____>26 days

- ____27-29 days
- ____30-32
- ____>32 days
- ____Don't know

F8. Can you characterize your daughter's usual period flow during the last year?

- ___Light
- ____Medium
- ____Heavy
- ____Don't know

F9. When was your daughter's last period before this study blood draw?

Date:__

____Don't know

F10. Has your daughter ever been pregnant?

____Yes

____No \rightarrow go to Section F

____Don't Know \rightarrow go to Section F

____Refused to answer \rightarrow go to Section F

F11. How many times has your daughter been pregnant?

	Pregnancy #1	Pregnancy #2	Pregnancy #3
a. What month and year did this pregnancy start?	/	/	/
b. What month and year did this pregnancy end?	/	/	/
c. Did the pregnancy result in a live birth?	Yes	Yes	Yes
	No (go to g)	No (go to g)	No (go to g)
	Don't Know	Don't Know	Don't Know
d. Did your daughter breastfeed the child?	Yes	Yes	Yes
	No (go to g)	No (go to g)	No (go to g)
	Don't Know	Don't Know	Don't Know
e. How long did your daughter breastfeed the child?	months	months	months
f. When did your daughter stop breastfeeding the			
child?	monthyear	monthyear	monthyear
g. Did a doctor or nurse say that your daughter had	Yes	Yes	Yes
pre-eclampsia during her pregnancy?	No	No	No
	Don't know	Don't know	Don't know
h. Did a doctor or nurse say that your daughter had	Yes	Yes	Yes
pregnancy-induced hypertension?	No	No	No
	Don't know	Don't know	Don't know
i. Did a doctor or nurse say that your daughter had	Yes	Yes	Yes
gestational diabetes?	No	No	No

Don't know	Don't know	Don't know

Section G. Mother's Pregnancy History

Starting with the pregnancy of your child in this study (Pregnancy 1), and including up to three of [your/the birth mother's] previous pregnancies, please fill out the table below. Circle the appropriate response.

	Pregnancy 1	Pregnancy 2	Pregnancy 3	Pregnancy 4
a. What month and	/	/	/	/
year did this				
pregnancy start?				
b. What month and	/	/	/	/
year did this				
pregnancy end?	Voc	Voc	Voc	Voc
c. Did the pregnancy	res	res	res	res
	No (go to g)	No (go to g)	No (go to g)	No (go to g)
	Don't Know	Don't Know	Don't Know	Don't Know
d. Did [you/the	Yes	Yes	Yes	Yes
child's mother]	No \rightarrow go to Part j.	No \rightarrow go to Part j.	No \rightarrow go to Part j.	No \rightarrow go to Part j.

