Section B: Residential History and Drinking Water Exposures

B1. On average, how many 8 oz. cups of tap water or beverages prepared with tap water does your child currently drink per day at home?

____ cups

____Didn't drink tap water

____Don't know

____Refused to answer

Note: 1 cup = 8 oz.; 2 cups = 1 pint (16 oz.); 4 cups = 1 quart (32 oz.); 16 cups = 1 Gallon (128 oz.)

B2. Please fill out the table below for all residences that your child has lived.

Street Address, City, State	Your child's	Move in	Main source of
	average	(mm/yy)	tap water at
	consumption of		this address
	tap water per		(public water
	day (# cups) at		system or
	this address		private well?)

B3. When [you were/the child's birth mother was] pregnant with your child, on average how many 8

oz. cups of tap water or beverages prepared with tap water did [you/she] drink per day?

____ cups

___Didn't drink tap water

____Don't know

____Refused to answer

B4. When [you were/the child's birth mother was] breastfeeding your child, on average how many 8

- oz. cups of tap water or beverages prepared with tap water did [you/she] drink per day?
- ____ cups
- ____Didn't drink tap water
- ____Don't know
- ____Refused to answer
- ____Did not breastfeed my child

Section C: History of Potential Exposure Modifiers

This next set of questions is for the child's birth mother about the child. If you are not her, we can follow up after this interview with a quick phone call to complete the questionnaire.

- C1. Has your child ever had a blood transfusion?
- ____Yes ightarrow Please specify how many times your child had a blood transfusion______
- ___No →go to Question C3
- ___Don't know →go to Question C3
- ____Refused to answer →go to Question C3
- C2. When did your child last have a blood transfusion?

_____month/year

- C3. Has your child ever donated blood?
- ____Yes → Please specify how many times your child has donated blood______
- ___No \rightarrow go to Section D.
- ____Don't know \rightarrow go to Section D.
 - ___Refused to answer \rightarrow go to Section D.
- C4. When did your child last donate blood? _____ Month/Year

C5. On average, how often does your child donate blood in a year?

Section D: Occupational History of the Child

This next set of questions is for the child's birth mother about the child. If you are not her, we can follow up after this interview with a quick phone call to complete the questionnaire.

D1. Has your child been employed for at least one month at a job?

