____Yes

___No \rightarrow go to Section E.

Job information	Job 1	Job 2	Job 3
a. Where did your child work?			
(City, State)			
b. Name of employer			
c. Start date (month, year)			
d. End date (month, year)			
e. Job title/description			
f. Did your child work with or around radiation or any chemicals at this job such as solvents, metals,	Yes (Please specify)	Yes (Please specify)	Yes (Please specify) No
asbestos, or pesticides?	Don't know	on't know	Don't know

D2. On average how many 8 oz. cups of tap water or beverages prepared with tap water did [he/she] drink per day at work?

____ cups

____Didn't drink tap water

____Don't know

____Refused to answer

Note: 1 cup = 8 oz.; 2 cups = 1 pint (16 oz.); 4 cups = 1 quart (32 oz.); 16 cups = 1 Gallon (128 oz.)

Section E: Child's Daycare/School History

E1. Did your child attend day care?

____Yes

No \rightarrow go to Question E3

____Don't know \rightarrow go to Question E3

_____Refused to answer \rightarrow go to Question E3

E2. Please fill out the table below for the day care centers your child attended.

Day care (name)	Street Address, City, State	Start Date (mm/yy)	End Date (mm/yy)	Child's average consumption of tap water per day (# cups)

Note: 1 cup = 8 oz.; 2 cups = 1 pint (16 oz.); 4 cups = 1 quart (32 oz.); 16 cups = 1 Gallon (128 oz.)

E3. Please fill out the table below for the schools your child has attended. If your child was home schooled, please go to Section F

School (name)	Street Address, City, State	Start	End	Child's average
		Date	Date	consumption of tap
		(mm/yy)	(mm/yy)	water per day (# cups)

Note: 1 cup = 8 oz.; 2 cups = 1 pint (16 oz.); 4 cups = 1 quart (32 oz.); 16 cups = 1 Gallon (128 oz.)

Section F: Child's Medical History

F1. Have you ever been told by a doctor or other health care provider that your child has or had any of the following medical conditions? Fill out the table below. Circle appropriate response and ask the respondent to specify as directed.

	Medical condition		If yes, what year was your child diagnosed?
a.	Cancer?	Yes (Please specify) No Don't know	year
b.	Allergies?	Yes (Please specify) No Don't know	year
C.	Atopic dermatitis/eczema?	Yes (Please specify) No Don't know	year
d.	Asthma?	Yes No Don't know	year
e.	Chronic stuffy/runny nose (rhinitis/sinusitis)?	Yes No Don't know	year
f.	High cholesterol?	Yes No Don't know	year
g.	Thyroid disease?	Yes (Please specify) No Don't know	year
h.	Delayed puberty?	Yes (Please specify) No Don't know	year

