i.	Obesity?	Yes No Don't know	year
j.	Lupus	Yes No Don't know	year
k.	Celiac disease	Yes No Don't know	year
I.	Crohn's disease	Yes No Don't know	year
m.	Diabetes	Yes, Type 1 Yes, Type 2 Yes, Type unknown No Don't know	year

	Medical condition		If yes, what year was your child diagnosed?
n.	Scleroderma	Yes No Don't know	year
0.	Attention deficit hyperactivity disorder (ADHD) or attention deficit disorder (ADD)?	Yes No → go to p Don't know → go to p	year
р.	How is your child treated for ADHD or ADD?		year
q.	Other learning or behavioral problems?	Yes (Please specify) No → go to Question B2. Don't know → go to Question B2.	year
r.	How is your child treated for their learning or behavioral problems?		

F2.. What age was your child last vaccinated for:

Diphtheria, Tetanus, Pertussis ("DTaP")	age	Don't know	never was vaccinated
"Tdap" booster Tetanus, Diptheria, Pertussis	sage	Don't know	never was vaccinated
Measles, Mumps, Rubella ("MMR")	age	Don't know	never was vaccinated
Tetanus shot (for a puncture wound or cut)	age	Don't know	never was vaccinated

FOR GIRLS ONLY

F3. Has your daughter ever used an oral contraceptive ("birth control pill")?

- ____Yes
- ___No → go to Question E5
- ____Don't know \rightarrow go to Question E5
- ____Refused to answer \rightarrow go to Question E5

F4. When did your daughter last use an oral contraceptive ("birth control pill")?

__Month/Year

F5. At what age did your daughter begin menstruation (have her first period)?

____Age

____Has not yet begun to menstruate \rightarrow go to Section G

___Don't know

F6. Does your daughter's period occur regularly (every month)?

___Yes

- ____No, it is irregular
- ____No, she does not have a period \rightarrow go to Question E10
- ____Don't know \rightarrow go to Question E10
- F7. How many days has been your daughter's cycle on average during the last year?
- ____>26 days
- ____27-29 days
- ____30-32
- ____>32 days
- ____Don't know
- F8. Can you characterize your daughter's usual period flow during the last year?
- ___Light
- ____Medium
- ____Heavy
- ____Don't know
- F9. When was your daughter's last period before this study blood draw? Date:
 - __Don't know
- F10. Has your daughter ever been pregnant?
- ___Yes
- ___No → go to Section G
- ____Don't Know \rightarrow go to Section G
- ____Refused to answer \rightarrow go to Section G

F11. How many times has your daughter been pregnant?

	Pregnancy #1	Pregnancy #2	Pregnancy #3
a. What month and year did this pregnancy start?	/	/	/

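### Several skip instructions in the child questionnaires point to missing or earlier items; followed as written, the short form bypasses age at menarche and vaccination ages

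*Protocol*

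**What the plan says.** Section 3.6.5.1 provides two versions of the child questionnaire: a long form (Attachment 15) when the parent is not an adult participant, and a short form (Attachment 15a) when the parent is.

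**Short form**
- F1q (other learning or behavioural problems) has the route "No → go to Question B2. Don't know → go to Question B2". The target reads "B2. Please fill out the table below for all residences that your child has lived". The item printed after the F1 table is F2: "What age was your child last vaccinated for", followed by a list of vaccines.
- F3 (ever used an oral contraceptive) has "No → go to Question E5", with the same target for Don't know and Refused. F6 sends girls with no period, and Don't know, to E10. The last item in Section E is "E3. Please fill out the table below for the schools your child has attended".

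**Long form**
- F10 (daughter ever pregnant) gives "go to Section F" for No, Don't Know and Refused.
- Section G item d (mother breastfed) sends No to Part j. The table runs from a to i.

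**Both forms**
- F1o (ADHD or ADD) sends No and Don't know to p, which asks how that condition is treated.

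Among the outcomes in Section 2.5.2, child hypothesis 6 lists "insulin-like growth factor - 1 (IGF-1), age at menarche, delayed" puberty. Child hypothesis 7 includes lower antibody responses to named vaccines. Section 3.6.5.1 assigns both vaccination history and age at first period to the questionnaire.

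**The concern.** A skip instruction is an operative rule of data collection: it decides who is asked what. Here some targets do not exist and others lead back to sections already completed. The items passed over include the study's source for one child outcome (age at menarche) and information needed to interpret another group (vaccine antibodies, where time since the last dose matters). The child medical record abstraction form (Attachment 17b) lists neither age at menarche nor vaccination, so it is no backup for either. If sites handle the faulty routes differently, completeness would vary by site and by form for reasons unrelated to the child.

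**Working it through.** No sample size, power or error rate is involved. The check traces each skip to its target and asks whether the target exists, whether it lies ahead, and what is passed over.

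| Form, item and answer | Stated target | What the target is | Passed over if followed literally |
|---|---|---|---|
| Short F1q, No or Don't know | B2 | Residence table, already completed | F2 (vaccination ages) and the rest of Section F |
| Short F3, No, Don't know or Refused | E5 | Does not exist; E ends at E3 | F5 (age at menarche) |
| Short F6, no period or Don't know | E10 | Does not exist | F10 and F11 (daughter's pregnancies) |
| Long G-d, No | Part j | Does not exist; table ends at i | g to i (pre-eclampsia, pregnancy-induced hypertension, gestational diabetes) |
| Long F10, No, Don't Know or Refused | Section F | The section in progress | Loops back instead of moving on to Section G |
| Both F1o, No or Don't know | p | ADHD treatment, the next item | Nothing; an inapplicable question is asked |

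**Could this be a fault in reading the PDF?** The forms contain their own answer key, so this is unlikely.
- The long form routes the same items correctly: F1q to F2, F3 to F5, F6 to F10.
- The short form routes F10 No to its Section G.
- In both forms the daughter's pregnancy table sends a pregnancy without breastfeeding to g.
- In the long form's Section G, item c sends a pregnancy without a live birth to g. The complication items are thus asked of pregnancies with no breastfeeding at all, and Part j cannot be the intended target for a live birth that was not breastfed.

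The short-form targets look like leftovers from another numbering.

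**Who is affected?** Under the literal route, short-form vaccination ages are reached only when another learning or behavioural problem is reported. Short-form age at menarche is not reached from F3 unless oral contraceptive use is reported. In the long form both routes are sound.

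**Can the loss be sized?** The target is 2,000 children, equally of both sexes, so 2,000 × 0.5 = 1,000 girls over both forms. The documents do not say how many will have the short form, how many will have reached menarche, or how often staff would correct the route. The 1,000 is only a ceiling on the girls who could be affected, not an estimate.

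**The case against.** The strongest reply is that these are proofreading slips that staff would catch. The forms carry interviewer wording, staff are trained in administering them (Section 3.6), and data entry from hardcopy is double (Section 3.8.4). The faults reveal themselves: E5, E10 and Part j are not there, and B2 and Section F return to answered questions. F5 is printed two items below F3. The reminder call (Attachment 8) asks parents to note vaccination dates. The forms still carry placeholder approval numbers.

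Much of this stands, and it limits what can be claimed. A reader might infer three stronger conclusions that the documents do not support:
- **The data would be lost for good because there is one visit.** The contact form (Attachment 10) announces possible later clarifying questions, and Section 3.8.4 has ATSDR and study staff resolve missing values. Nor do the documents describe electronic routing that would enforce a wrong target.
- **The Part j fault makes missingness depend on exposure, because breastfeeding is a PFAS elimination route.** The breastfeeding answer itself is recorded at d. Items g to i are background data about a mother who is not an adult participant and serve no stated child endpoint; hypertensive disorders of pregnancy belong to the adult hypotheses.
- **A percentage of missing data can be given.** The documents supply no share of births not breastfed and no rate at which staff would miss a fault.

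The reply does not remove the point. Section 3.6 provides a space for completing the questionnaire, with staff available for questions, so correction by an interviewer is not assured. About six recipients are expected (Section 1.2), and each would have to improvise. The website flyer and the Manual of Procedures are marked as unfinished; the questionnaires carry no such mark.

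**Conclusion.** The skip targets are wrong as printed. Followed literally, the short form bypasses data for one stated child outcome (age at menarche) and data needed to interpret the vaccine antibody outcomes. Short-form F6 also passes over the daughter's own pregnancy items. The long-form faults matter less: Part j costs background data on maternal complications, and F10 loops. F1o is a nuisance without data loss.

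The size of any loss cannot be stated, since it depends on how often staff follow the printed route and how much recontact recovers. The conclusion rests only on the printed routes and on the parallel items that show what was intended. The error concerns the instruments and does not touch the design, hypotheses or analysis. It should still be corrected before the first family is interviewed, because correction then is far cheaper than recontact.

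**What to change.** Correct the targets:
- Short form: F1q No and Don't know to F2; F3 No, Don't know and Refused to F5; F6 no period and Don't know to F10.
- Long form: Section G item d No to g; F10 No, Don't Know and Refused to Section G.
- Both forms: F1o No and Don't know to q.

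Then test-run both forms on a boy, a premenarchal girl, a menstruating girl who has never been pregnant, and a child who was not breastfed, confirming that every intended item is reached. The long-form run should include a family with no further addresses: B8 No leads to Section C, an existing target that lies beyond B10 and B11 on the mother's tap water intake. That route is separate from the point made here but can be settled at the same time.

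The cost is editing the forms before approval and a short test, with no new items and no added staff.

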Attachment 7a. Appointment Reminder Card and Instructions

Multi-site PFAS Health Study Appointment Reminder Card

Clinic Visit

	Appointment Information for Your Multi-site Study Interview
	[NAME OF LOCATION]
	[Street Address]
	[Local or Toll Free Telephone Number]
	Day:
	Date: ////
	Time: : AM PM
	Study ID No.:
	Please bring this paper with you.
We will draw a blo	od sample so please do not eat for at least 8 hours before your appointment. You may drink water during this time.
Don't forget to c	ollect your urine sample in the morning. Bring your urine sample with you.
	If you take diabetic medication, see special instructions. Don't forget to bring all your medication for us to see.
[If you ar	e a past participant in the [insert site] PFAS Blood Testing Program, please bring a copy of your results report.]
	If you are unable to keep this appointment, please call to set up another time.
	Toll-free (xxx)xxx-xxxx

Multi-site PFAS Study Appointment Reminder Card

Home Visit				
Appointment Information for Your Multi-site PFAS Study Interview				
We will arrive at your home on the date and time below:				
Day:				
Date: / /				
Time: : 🗆 AM 🗆 PM				
Study ID No.:				
We will draw a blood sample so please do not eat for at least 8 hours before your appointment. You may drink water during this time.				
Don't forget to collect your urine sample in the morning.				
If you take diabetic medication, see special instructions. Don't forget to gather all your medication for us to see.				
[If you are a past participant in the [insert site] PFAS Blood Testing Program, please provide a copy of your results report.]				
If you are unable to keep this appointment, please call to set up another time.				
Toll-free (xxx)xxx-xxxx				

Multi-site Study Appointment Reminder Card – Instructions

Instructions for Study Participants

On the day of your appointment

Fasting: Do not eat or drink for at least 8 hours before your appointment. Do not have candy, gum, or soda. Drinking water is fine. Take all your medications with water only.

If you have diabetes and take insulin or other medications, we will schedule your appointment as early in the morning as possible. Please fast for at least 8 hours if your meal and medication plan allows. If you must eat before your appointment, please eat fat-free or low-fat items and take your medications as usual. Write down what you ate and when you ate it.

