ATSDR estimates the average public reporting burden for this of instructions, searching existing data/information sources, gath the collection of information. An agency may not conduct or sp displays a currently valid OMB Control Number. Send commen including suggestions for reducing this burden to CDC/ATSDR I 30333; ATTN: PRA (0923-xxxx).	collection of information as 10 minutes per re ering and maintaining the data/information oonsor, and a person is not required to respo ts regarding this burden estimate or any oth nformation Collection Review Office, 1600 Cl	esponse, including the time for reviewing needed, and completing and reviewing and to a collection of information unless it er aspect of this collection of information, lifton Road NE, MS D-74, Atlanta, Georgia
Adult Study ID No.:	OR Child Study ID No.: _	
You were asked to collect a first morning v	oid urine sample when you got	up today.
1. Did you bring it today?		🗆 Yes 🗆 No
1a. [IF NO] Can you give us a sample	e now?	🗌 Yes 🗌 No
2. Result of the urine collection (mark one)	Volume	
Complete	(at least 10-mL)	
Partial	2a. (mL)	
Unable to collect		
Before we can take [your/your child's] blo [you/your child] can provide a blood samp	od we need to ask you a few qu le.	estions on whether
3. [Do you/Does your child] have hemophilia?		🗆 Yes 🗖 No
4. [Have you/Has your child] received any c	hemotherapy in the last four we	eks? 🗌 Yes 🗌 No
5. [Do you/Does your child] have active som arm/shoulder that could prevent us from	es, disease, or other problem on n taking a blood sample*?	the 🗌 Yes 🗌 No
* This may include gauze dressings casts ed	ema naralysis tubes onen sores o	wounds withered arms or

* This may include gauze dressings, casts, edema, paralysis, tubes, open sores or wounds, withered arms or limbs missing, damaged, sclerosed or occluded veins, allergies to cleansing reagents, burned or scarred tissue, shunt or intravenous lines on both arms. Please check and review all with the participant.
[IF THE ADULT/PARENT OR GUARDIAN RESPONDED 'YES' TO ANY OF THE ABOVE QUESTIONS, THE PARTICIPANT SHOULD BE EXCLUDED FROM THE BLOOD DRAW. PLEASE SEE STUDY COORDINATOR IMMEDIATELY.

SENIOR SUPERVISING NURSE WILL MAKE THE DECISION WHETHER A PARTICIPANT WITH ANY TYPE OF SHOULDER LESIONS CAN SAFELY PROVIDE A BLOOD SAMPLE]

We also want to ask you a few more questions as a precaution.

5. [Are you/Is your child] on blood thinning medication?		🗆 Yes 🗆 No
7. Are you on diabetes medication or insulin?		🗆 Yes 🗌 No

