8. Tell me the last time you ate. Was it less than	n eight hours ago?	🗆 Yes 🗌 No
8a. [IF YES] How long ago did you eat?	: (hours and minutes)	
8b and what did you eat?	I	
[IF THE PARTICIPANT ANSWERED 'YES' TO ANY COORDINATOR AND SUPERVISING NURSE TO M	OF THE ABOVE QUESTIONS PLEASE SEE S IAKE SURE THEY CAN SAFELY PROVIDE BI	TUDY LOOD SAMPLE]
9. Result of the Blood Draw (mark one)	Volume	
□ Complete	(35-mL adults/25 ml children)	
Partial	7a. (mL)	
Unable to collect		
9a. Date: _ / / 9b. Tin	ne: _ : 🗆 AM 🗆 PM	
9c. Code Partial/Inability to Collect (circle one)		
Reason for partial or inability to collect blood:		
 Pregnant Medical (e.g. patient frail, weak, lost consciousness) Refused 		
4. Other (describe)		

NOTES: Care should be used in drawing blood from all subjects. Common adverse effects include bruising, bleeding, and fainting. Please ask all participants whether they prefer to lie down to have blood drawn.

Ask everyone if they tend to faint when giving blood. Suggest they sit down for five minutes after giving blood.

Fasting diabetic participants who use insulin will be given priority appointments for their blood draw.

Light snacks will be provided following blood collection.

See Protocol Attachment 14 (Manual of Operations) for further details on collecting blood samples.

[ON INVESTIGATORS INSTITUTION LETTERHEAD] [DATE]

[NAME OF PROVIDER] [ADDRESS] [CITY, STATE ZIP CODE]

Subject: Medical verification and records review for Multi-site PFAS Health Study

Dear [NAME OF PROVIDER]:

The Agency for Toxic Substances and Disease Registry (ATSDR) and [insert institution name] are conducting a research study of the health effects from exposure to per- and polyfluoroalkyl substances (PFAS) found in drinking water. We are working with the assistance of your local health department [insert name] and [name of all other partners]. ATSDR and research partners are conducting this research study with oversight from the CDC/ATSDR Institutional Review Board (IRB) under CDC Protocol No. xxxxxxx.

Under Section 8006 of the 2018 Consolidated Appropriations Act, Congress authorized ATSDR to study the impact that exposure to PFAS in drinking water might have on the health of affected citizens. This study will see if there is an increase of symptoms or illness related to these chemicals.

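### Attachment 14 omits the child alternative from its diabetes-medicine and fasting items and asks only about food, so fasting status may be misclassified

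*Protocol*

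**What the plan says.** Attachment 14 (printed after Attachment 15a) takes either an adult or a child study ID. Most of its blood-draw questions are worded for both cases, for example "Do you/Does your child] have hemophilia" and "Are you/Is your child] on blood thinning medication". The diabetes-medicine question, item 7, is not: "Are you on diabetes medication or insulin". Nor is the fasting question, item 8, which opens "Tell me the last time you ate" and asks whether that was less than eight hours ago. Only if the answer is yes do the follow-ups apply: "How long ago did you eat" (8a) and "and what did you eat" (8b).

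Two staff instructions on the form name the respondent differently. The one closing the exclusion questions begins "IF THE ADULT/PARENT OR GUARDIAN RESPONDED 'YES' TO ANY OF THE ABOVE QUESTIONS". The one after item 8 speaks of the participant as having answered.

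On fasting itself, the instruction sheet in Attachment 7a says "Do not eat or drink for at least 8 hours before your appointment", rules out soda, gum and candy, and permits water. The face of the reminder card and the reminder call in Attachment 8 tell people not to eat and say that water is allowed; they name no other drink.

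Section 3.6.4 assigns the recording of fasting status to this form and accepts that some participants will not manage to fast.

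**The concern.** A parent who has just been asked whether the child takes blood thinners is next asked about diabetes medicine and the last meal, with the child no longer mentioned. Taken literally, the answers describe the parent and are filed under the child's ID. For a long-form child (Attachment 15) the parent is not a study participant, so the parent's own meals need not follow the child's fast.

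The second gap applies at any age. Someone who had juice, milk or soda within eight hours, but no food, can truthfully answer no to item 8 and is recorded as fasting.

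At stake is a covariate that has to be captured on the day. Section 2.5.2 puts triglycerides, LDL, glucose and insulin among both the child and the adult hypotheses. Section 3.7 measures them in fasting serum, and Attachment 2 labels the lipids and glucose as fasting tests. A last-meal time that is missed or misattributed at the draw cannot be reliably recovered later. Attachment 21 also returns results to families with out-of-range values marked, and its lipid and glucose rows are labelled as fasting.

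**Working it through.** No stated figure depends on this wording, so the check is a comparison of texts.

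**Step 1. Wording of the blood-draw questions in Attachment 14**

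| Question | Child alternative? |
|---|---|
| Hemophilia | Yes |
| Chemotherapy | Yes |
| Arm or shoulder problem | Yes |
| Blood thinners | Yes |
| Item 7, diabetes medicine | No |
| Item 8, last meal | No |
| Item 8a, how long ago | No |
| Item 8b, what was eaten | No |

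All 4 diabetes-medicine and fasting prompts lack the alternative; all 4 other blood-draw questions carry it. The reminder call in Attachment 8 does use child wording for diabetes medicine, so the omission looks like an oversight and not a choice.

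**Step 2. Food and drink**

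| Place | Food | Drinks other than water |
|---|---|---|
| Attachment 7a, instruction sheet | Barred | Barred |
| Attachment 7a, card face | Barred | Not mentioned; water allowed |
| Attachment 8, reminder call | Barred | Not mentioned; water allowed |
| Attachment 14, items 8, 8a, 8b | Asked | Not asked |

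None of the 3 fasting prompts (0 of 3) asks about drinks.

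**Step 3. What the form would record**

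- Child fasted, parent ate within eight hours, parent answers for himself or herself: recorded as not fasting, wrongly.
- Child ate within eight hours, parent did not, parent answers for himself or herself: recorded as fasting, wrongly.
- Parent and child both fasted: recorded correctly, whoever is meant.
- Any participant with a non-water drink but no food within eight hours: item 8 is answered no, 8a and 8b are skipped, and no trace of the drink remains.

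**Step 4. Is the information held elsewhere?** The appointment tracking form (Attachment 9), the medication list (Attachment 11) and the body-measures form (Attachment 13) have no field for the last meal. Attachments 7a and 8 ask people on diabetes medication who cannot fast to write down what and when they ate, which covers that subgroup only. Diabetes medicine is better backed up: the reminder call asks about it with child wording, Attachment 11 lists medicines under a child ID, and item F1 of both child questionnaires asks about diabetes by type.

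**The case against.** The best reply is that nobody would misread the form in practice. The instruction after item 8 says the participant answered, and on a child's form the participant is the child. The urine questions at the top also say only you, and no one would take them to ask for the parent's urine. Section 3.6.4 makes clear that the participant's fasting status is meant, the lead-in to the questions refers to the child's blood, and Section 3.6 promises trained staff. An older child may answer directly. The protocol's analysis section describes no fasting-only analysis, and the Manual of Procedures (Attachment 12) is still a placeholder.

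Much of this stands. A reader might infer that children's fasting status is recorded wrongly as a matter of course. The documents do not support that; they show a risk that depends on who answers and how staff put the question. A reader might also infer that all 2,000 children, or all 8,000 participants, are affected. Those are recruitment targets and count only the people to whom the form is put. Nor is the form the sole trace of a broken fast in every case, given the written meal notes asked of some people on diabetes medication.

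The reply does not remove the point. The two staff instructions disagree about the respondent, participants may be as young as 4, and nothing in the document tells staff to reword these items. The omission of drinks does not depend on the respondent at all.

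**Conclusion.** The point holds as a wording defect that creates a risk of misclassification, not as a demonstrated error. Two groups are exposed: children whose parent answers items 7 to 8b for himself or herself, and participants of any age who had a non-water drink but no food within eight hours. The outcomes concerned are fasting glucose, insulin, triglycerides and LDL. Item 7 matters less, because diabetes medicine is recorded elsewhere; the fasting items have only partial backup.

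The size cannot be given. The documents contain no rate of literal answering, of discordant meals between parent and child, or of non-water drinks before the visit, and any figure would be an assumption. No sample size or power figure changes. Correction before the form is used is worthwhile because it is nearly free and the information cannot be reliably recovered afterwards.

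**What to change.** In Attachment 14:

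- Item 7: *[Are you/Is your child] on diabetes medication or insulin?*
- Item 8: *When did [you/your child] last eat or drink anything other than water? Was it less than eight hours ago?*
- Items 8a and 8b: the same change of subject, covering food and drink.
- Make the two staff instructions name the respondent in the same way.

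Then reconcile the fasting wording of the Attachment 7a instruction sheet, the card face, the Attachment 8 call and the form, so that participants are told and asked the same thing. Which fasting rule applies is for the investigators; recording both food and drink lets either be applied at analysis.

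The cost is new wording for four items and light edits to the card, the script and the staff instructions. Attachment 5c lists IRB and OMB approvals as pending, and no visit time of any consequence is added.
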